#### INAS-VIPOS Statistical Analysis Plan V02-00

Supporting document SOP BMT 01.09 - Doc 5002.02 - Effective date 21.03.2017

Section C-2.5	Incidence rate of clinically relevant anemia for long-term use, AT population, Complete cohort
Table C-2.5.1	Incidence rate of clinically relevant anemia for long-term use, AT population, Starter
Table C-2.5.2	Incidence rate of clinically relevant anemia for long-term use, AT population, Switcher
Table C-2.5.3	Incidence rate of clinically relevant anemia for long-term use, AT population, Restarter
Table C-2.5.4	Incidence rate of clinically relevant anemia for long-term use, AT population, Diagnosis confirmed by surgery
Table C-2.5.5	Incidence rate of clinically relevant anemia for long-term use, AT population, Diagnosis based on clinical symptoms
Table C-2.5.6	Incidence rate of clinically relevant anemia for long-term use, AT population, Germany
Table C-2.5.7	Incidence rate of clinically relevant anemia for long-term use, AT population, Poland
Table C-2.5.8	Incidence rate of clinically relevant anemia for long-term use, AT population, Hungary
Table C-2.5.9	Incidence rate of clinically relevant anemia for long-term use, AT population, Switzerland
Table C-2.5.10	Incidence rate of clinically relevant anemia for long-term use, AT population, Russia
Table C-2.5.11	Incidence rate of clinically relevant anemia for long-term use, AT population, Ukraine
Section C-2.6	Incidence rate of new depression or worsening of existing depression for long-term use
Table C-2.6.1	Incidence rate of new depression or worsening of existing depression for long-term use, AT population, Complete cohort
Table C-2.6.2	Incidence rate of new depression or worsening of existing depression for long-term use, AT population, Starter
Table C-2.6.3	Incidence rate of new depression or worsening of existing depression for long-term use, AT population, Switcher
Table C-2.6.4	Incidence rate of new depression or worsening of existing depression for long-term use, AT population, Restarter
Table C-2.6.5	Incidence rate of new depression or worsening of existing depression for long-term use, AT population, Diagnosis confirmed by surgery
Table C-2.6.6	Incidence rate of new depression or worsening of existing depression for long-term use, AT population, Diagnosis based on clinical symptoms
Table C-2.6.7	Incidence rate of new depression or worsening of existing depression for long-term use, AT population, Germany

Incidence rate of new depression or worsening of existing depression for long-term use, AT population, Poland

Table C-2.6.9 Incidence rate of new depression or worsening of existing depression for long-term use, AT population, Hungary

Table C-2.6.10 Incidence rate of new depression or worsening of existing depression for long-term use, AT population, Switzerland
Table C-2.6.11 Incidence rate of new depression or worsening of existing depression for long-term use, AT population, Russia
Table C-2.6.12 Incidence rate of new depression or worsening of existing depression for long-term use, AT population, Ukraine
Section C-2.7 Incidence proportions of treatment discontinuation for long-term use
Table C-2.7.1 Incidence proportions of treatment discontinuation for long-term use, AT population, Complete cohort
Table C-2.7.2 Incidence proportions of treatment discontinuation for long-term use, AT population, Starter
Table C-2.7.3 Incidence proportions of treatment discontinuation for long-term use, AT population, Switcher
Table C-2.7.4 Incidence proportions of treatment discontinuation for long-term use, AT population, Restarter
Table C-2.7.5 Incidence proportions of treatment discontinuation for long-term use, AT population, Diagnosis confirmed by surgery
Table C-2.7.6 Incidence proportions of treatment discontinuation for long-term use, AT population, Diagnosis based on clinical symptoms
Table C-2.7.7 Incidence proportions of treatment discontinuation for long-term use, AT population, Germany
Table C-2.7.8 Incidence proportions of treatment discontinuation for long-term use, AT population, Poland
Table C-2.7.9 Incidence proportions of treatment discontinuation for long-term use, AT population, Hungary
Table C-2.7.10 Incidence proportions of treatment discontinuation for long-term use, AT population, Switzerland
Table C-2.7.11 Incidence proportions of treatment discontinuation for long-term use, AT population, Russia
Table C-2.7.12 Incidence proportions of treatment discontinuation for long-term use, AT population, Ukraine

Supporting document SOP BMT 01.09 – Doc 5002.02 – Effective date 21.03.2017

#### Section C-3 Other safety outcomes

#### Section C-3.1 Incidence rate of confirmed thromboembolic events

Table C-3.1.1 Incidence rate of confirmed thromboembolic events, AT population, Complete cohort

	DNG		OAED			NAED		Ex-use	Allocation unknown	Total
		GnRH-a	Danazol	All OAED	СНС	Other progestin	All NAED			
Number of women years	xx	XX	XX	xx	xx	xx	xx	xx	XX	xx
ALL VTE & ATE	xx	xx	xx	XX	xx	XX	xx	xx	xx	xx
IR* (95% CI)	xx.x (xx.x-x.x)	xx.x (xx.x-x.x)	xx.x (xx.x-x.x)	xx.x (xx.x-x.x)	xx.x (xx.x-x.x)					
Thereof										
All VTE	xx	xx	xx	xx	xx	xx	xx	xx	xx	xx
	xx.x (xx.x-x.x)	xx.x (xx.x-x.x)	xx.x (xx.x-x.x)	xx.x (xx.x-x.x)	xx.x (xx.x-x.x)					
Thereof										
PE	xx	xx	xx	xx	xx	xx	xx	xx	xx	xx
	xx.x (xx.x-x.x)	xx.x (xx.x-x.x)	xx.x (xx.x-x.x)	xx.x (xx.x-x.x)	xx.x (xx.x–x.x)	xx.x (xx.x-x.x)	xx.x (xx.x-x.x)	xx.x (xx.x-x.x)	xx.x (xx.x-x.x)	xx.x (xx.x-x.x)
ALL ATE (TIAs included)	xx	xx	xx	XX	xx	XX	XX	XX	xx	xx
	xx.x (xx.x-x.x)	xx.x (xx.x-x.x)	xx.x (xx.x-x.x)	xx.x (xx.x-x.x)	xx.x (xx.x-x.x)					
Thereof										
AMI										
Ischemic stroke										
TIA										
ALL ATE (TIAs excluded)										

Note: \* Incidence rate is shown per 10^4 women years.

Table C-3.1.2	Incidence rate of confirmed thromboembolic events, AT population, Starter
Table C-3.1.3	Incidence rate of confirmed thromboembolic events, AT population, Switcher
Table C-3.1.4	Incidence rate of confirmed thromboembolic events, AT population, Restarter
Table C-3.1.5	Incidence rate of confirmed thromboembolic events, AT population, Diagnosis confirmed by surgery
Table C-3.1.6	Incidence rate of confirmed thromboembolic events, AT population, Diagnosis based on clinical symptoms
Table C-3.1.7	Incidence rate of confirmed thromboembolic events, AT population, Germany
Table C-3.1.8	Incidence rate of confirmed thromboembolic events, AT population, Poland
Table C-3.1.9	Incidence rate of confirmed thromboembolic events, AT population, Hungary
Table C-3.1.10	Incidence rate of confirmed thromboembolic events, AT population, Switzerland
Table C-3.1.11	Incidence rate of confirmed thromboembolic events, AT population, Russia
Table C-3.1.12	Incidence rate of confirmed thromboembolic events, AT population, Ukraine

Supporting document SOP BMT 01.09 – Doc 5002.02 – Effective date 21.03.2017

#### Section C-3.2 Incidence rate of fatal cases (all deaths)

Table C-3.2.1 Incidence rate of fatal cases (all deaths), AT population, Complete cohort

	DNG		OAED		NAED		Ex-use	Allocation unknown	Total	
		GnRH-a	Danazol	All OAED	CHC	Other progestin	All NAED			
Number of women years	xx									
All deaths  IR* (95% CI)	xx xx.x (xx.x–x.x)									
Reason << Category >>	xx xx.x (xx.x–x.x)	xx xx.x (xx.x–x.x)		xx xx.x (xx.x–x.x)	xx xx.x (xx.x–x.x)	xx xx.x (xx.x–x.x)	xx xx.x (xx.x-x.x)	xx xx.x (xx.x–x.x)	xx xx.x (xx.x–x.x)	xx xx.x (xx.x–x.x)

Note: \* Incidence rate is shown per 10^4 women years.

Table C-3.2.2	Incidence rate of fatal cases (all deaths), AT population, Starter
Table C-3.2.3	Incidence rate of fatal cases (all deaths), AT population, Switcher
Table C-3.2.4	Incidence rate of fatal cases (all deaths), AT population, Restarter
Table C-3.2.5	Incidence rate of fatal cases (all deaths), AT population, Diagnosis confirmed by surgery
Table C-3.2.6	Incidence rate of fatal cases (all deaths), AT population, Diagnosis based on clinical symptoms
Table C-3.2.7	Incidence rate of fatal cases (all deaths), AT population, Germany
Table C-3.2.8	Incidence rate of fatal cases (all deaths), AT population, Poland
Table C-3.2.9	Incidence rate of fatal cases (all deaths), AT population, Hungary
Table C-3.2.10	Incidence rate of fatal cases (all deaths), AT population, Switzerland
Table C-3.2.11	Incidence rate of fatal cases (all deaths), AT population, Russia
Table C-3.2.12	Incidence rate of fatal cases (all deaths), AT population, Ukraine

Supporting document SOP BMT 01.09 – Doc 5002.02 – Effective date 21.03.2017

#### Section C-3.3 Incidence rate of serious adverse events by organ system

Table C-3.3.1 Incidence rate of serious adverse events by organ system, AT population, Complete cohort

	DNG		OAED		NAED		Ex-use	Allocation unknown	Total	
		GnRH-a	Danazol	All OAED	CHC	Other progestin	All NAED			
Number of women years	xx	xx	xx	xx	xx	xx	xx	xx	xx	xx
Serious adverse events*	xx	xx	xx	xx	xx	xx	XX	XX	xx	xx
IR** (95% CI) Thereof ***	xx.x (xx.x-x.x)	xx.x (xx.x–x.x)	xx.x (xx.x–x.x)	xx.x (xx.x-x.x)	xx.x (xx.x–x.x)	xx.x (xx.x–x.x)				
Infectious diseases	xx	xx	xx	xx	xx	xx	xx	xx	xx	xx
	xx.x (xx.x-x.x)	xx.x (xx.x-x.x)	xx.x (xx.x-x.x)	xx.x (xx.x-x.x)	xx.x (xx.x-x.x)					
Neoplasms, malignant	xx	xx	xx	xx	xx	xx	xx	xx	xx	xx
	xx.x (xx.x-x.x)	xx.x (xx.x-x.x)	xx.x (xx.x-x.x)	xx.x (xx.x-x.x)	xx.x (xx.x-x.x)					
Neoplasms, benign	xx	XX	XX	XX	xx	xx	XX	xx	XX	xx
	xx.x (xx.x-x.x)	xx.x (xx.x-x.x)	xx.x (xx.x-x.x)	xx.x (xx.x-x.x)	xx.x (xx.x-x.x)					
Blood	xx	xx	xx	XX	xx	XX	XX	xx	xx	xx
and blood-forming organs	xx.x (xx.x–x.x)	xx.x (xx.x–x.x)	xx.x (xx.x-x.x)	xx.x (xx.x-x.x)	xx.x (xx.x–x.x)					
Endocrine diseases	XX	xx	XX	xx	xx	xx	xx	xx	xx	xx
	xx.x (xx.x-x.x)	xx.x (xx.x-x.x)	xx.x (xx.x-x.x)	xx.x (xx.x-x.x)	xx.x (xx.x-x.x)					
Mental and	xx	xx	xx	XX	XX	XX	XX	xx	xx	xx
behavioral disorders	xx.x (xx.x-x.x)	xx.x (xx.x-x.x)	xx.x (xx.x-x.x)	xx.x (xx.x-x.x)	xx.x (xx.x-x.x)					
Disease of the nervous system	xx	xx	xx	xx	xx	xx	xx	xx	xx	xx
	xx.x (xx.x-x.x)	xx.x (xx.x-x.x)	xx.x (xx.x-x.x)	xx.x (xx.x-x.x)	xx.x (xx.x-x.x)					
Eye	xx	xx	xx	xx	xx	xx	XX	xx	xx	xx
	xx.x (xx.x-x.x)	xx.x (xx.x-x.x)	xx.x (xx.x-x.x)	xx.x (xx.x-x.x)	xx.x (xx.x-x.x)					
Ear	xx	xx	xx	xx	xx	xx	xx	xx	xx	xx
	xx.x (xx.x-x.x)	xx.x (xx.x-x.x)	xx.x (xx.x-x.x)	xx.x (xx.x-x.x)	xx.x (xx.x-x.x)					

Supporting document SOP BMT 01.09 – Doc 5002.02 – Effective date 21.03.2017

Cardiovascular system	xx	xx	xx	xx	xx	XX	xx	xx	xx	XX
caratovascatar system					xx.x (xx.x–x.x)					
Respiratory system	XX		XX (XX.X X.X)	XX	XX	XX (XX.X X.X)	XX (XX.X X.X)	XX	XX (XX.X X.X)	XX (XX.X X.X)
Respiratory system										
	xx.x (xx.x–x.x)	xx.x (xx.x–x.x)	xx.x (xx.x–x.x)	xx.x (xx.x–x.x)	xx.x (xx.x–x.x)	xx.x (xx.x–x.x)	xx.x (xx.x–x.x)	xx.x (xx.x–x.x)	xx.x (xx.x–x.x)	xx.x (xx.x–x.x)
Digestive system	XX	XX	XX	XX	XX	XX	XX	XX	XX	XX
	xx.x (xx.x-x.x)	xx.x (xx.x-x.x)	xx.x (xx.x-x.x)	xx.x (xx.x-x.x)	xx.x (xx.x-x.x)	xx.x (xx.x-x.x)	xx.x (xx.x-x.x)	xx.x (xx.x-x.x)	xx.x (xx.x-x.x)	xx.x (xx.x-x.x)
Skin	XX	XX	XX	XX	XX	XX	XX	XX	XX	XX
	xx.x (xx.x-x.x)	xx.x (xx.x-x.x)	xx.x (xx.x-x.x)	xx.x (xx.x-x.x)	xx.x (xx.x-x.x)	xx.x (xx.x-x.x)	xx.x (xx.x-x.x)	xx.x (xx.x-x.x)	xx.x (xx.x-x.x)	xx.x (xx.x-x.x)
Musculoskeletal	xx	xx	xx	xx	XX	xx	xx	xx	xx	xx
system and connective	xx.x (xx.x-x.x)	xx.x (xx.x-x.x)	xx.x (xx.x-x.x)	xx.x (xx.x-x.x)	xx.x (xx.x-x.x)	xx.x (xx.x-x.x)	xx.x (xx.x-x.x)	xx.x (xx.x-x.x)	xx.x (xx.x-x.x)	xx.x (xx.x-x.x)
tissue										
tissac										
Genitourinary system	XX	XX	xx	xx	xx	xx	XX	xx	xx	xx
					xx xx.x (xx.x–x.x)					
		xx.x (xx.x-x.x)				xx.x (xx.x-x.x)				
Genitourinary system	xx.x (xx.x-x.x) xx	xx.x (xx.x-x.x) xx	xx.x (xx.x-x.x) xx	xx.x (xx.x–x.x) xx	xx.x (xx.x-x.x)	xx.x (xx.x–x.x) xx	xx.x (xx.x–x.x) xx	xx.x (xx.x-x.x) xx	xx.x (xx.x–x.x) xx	xx.x (xx.x–x.x) xx
Genitourinary system  Pregnancy, delivery	xx.x (xx.x-x.x) xx	xx.x (xx.x-x.x) xx xx.x (xx.x-x.x)	xx.x (xx.x-x.x) xx	xx.x (xx.x–x.x) xx	xx.x (xx.x–x.x) xx	xx.x (xx.x-x.x) xx xx.x (xx.x-x.x)	xx.x (xx.x–x.x) xx	xx.x (xx.x-x.x) xx	xx.x (xx.x–x.x) xx	xx.x (xx.x–x.x) xx
Genitourinary system  Pregnancy, delivery  and puerperium*	xx.x (xx.x-x.x) xx xx.x (xx.x-x.x) xx	xx.x (xx.x-x.x) xx xx.x (xx.x-x.x) xx	xx.x (xx.x-x.x) xx xx.x (xx.x-x.x) xx	xx.x (xx.x-x.x) xx xx.x (xx.x-x.x) xx	xx.x (xx.x–x.x) xx xx.x (xx.x–x.x)	xx.x (xx.x-x.x) xx xx.x (xx.x-x.x) xx	xx.x (xx.x-x.x) xx xx.x (xx.x-x.x) xx	xx.x (xx.x-x.x) xx xx.x (xx.x-x.x) xx	xx.x (xx.x-x.x) xx xx.x (xx.x-x.x) xx	xx.x (xx.x-x.x) xx xx.x (xx.x-x.x) xx
Genitourinary system  Pregnancy, delivery  and puerperium*  Malformations,	xx.x (xx.x-x.x) xx xx.x (xx.x-x.x) xx	xx.x (xx.x-x.x) xx xx.x (xx.x-x.x) xx	xx.x (xx.x-x.x) xx xx.x (xx.x-x.x) xx	xx.x (xx.x-x.x) xx xx.x (xx.x-x.x) xx	xx.x (xx.x-x.x) xx xx.x (xx.x-x.x) xx	xx.x (xx.x-x.x) xx xx.x (xx.x-x.x) xx	xx.x (xx.x-x.x) xx xx.x (xx.x-x.x) xx	xx.x (xx.x-x.x) xx xx.x (xx.x-x.x) xx	xx.x (xx.x-x.x) xx xx.x (xx.x-x.x) xx	xx.x (xx.x-x.x) xx xx.x (xx.x-x.x) xx
Genitourinary system  Pregnancy, delivery and puerperium* Malformations, deformations and	xx.x (xx.x-x.x) xx xx.x (xx.x-x.x) xx	xx.x (xx.x-x.x) xx xx.x (xx.x-x.x) xx	xx.x (xx.x-x.x) xx xx.x (xx.x-x.x) xx	xx.x (xx.x-x.x) xx xx.x (xx.x-x.x) xx	xx.x (xx.x-x.x) xx xx.x (xx.x-x.x) xx	xx.x (xx.x-x.x) xx xx.x (xx.x-x.x) xx	xx.x (xx.x-x.x) xx xx.x (xx.x-x.x) xx	xx.x (xx.x-x.x) xx xx.x (xx.x-x.x) xx	xx.x (xx.x-x.x) xx xx.x (xx.x-x.x) xx	xx.x (xx.x-x.x) xx xx.x (xx.x-x.x) xx
Genitourinary system  Pregnancy, delivery and puerperium* Malformations, deformations and chromosomal	xx.x (xx.x-x.x) xx xx.x (xx.x-x.x) xx	xx.x (xx.x-x.x) xx xx.x (xx.x-x.x) xx xx.x (xx.x-x.x)	xx.x (xx.x-x.x) xx xx.x (xx.x-x.x) xx xx.x (xx.x-x.x)	xx.x (xx.x-x.x) xx xx.x (xx.x-x.x) xx	xx.x (xx.x-x.x) xx xx.x (xx.x-x.x) xx	xx.x (xx.x-x.x) xx xx.x (xx.x-x.x) xx xx.x (xx.x-x.x)	xx.x (xx.x-x.x) xx xx.x (xx.x-x.x) xx	xx.x (xx.x-x.x) xx xx.x (xx.x-x.x) xx	xx.x (xx.x-x.x) xx xx.x (xx.x-x.x) xx xx.x (xx.x-x.x)	xx.x (xx.x-x.x) xx xx.x (xx.x-x.x) xx xx.x (xx.x-x.x)

Note: \* SAEs, which occurred within 3 months after stop of EMT, were attributed to the last EMT used by the women. Therefore, pregnancy-related SAEs in XXX cohorts does not necessarily reflect unwanted pregnancies during EMT use.

Note: \*\* Incidence rate is shown per 104 women years.

Note: \*\*\* Women may appear in more than one category. ICD10 Codes Version 2009.

Table C-3.3.2	Incidence rate of serious adverse events by organ system, AT population, Starter
Table C-3.3.3	Incidence rate of serious adverse events by organ system, AT population, Switcher
Table C-3.3.4	Incidence rate of serious adverse events by organ system, AT population, Restarter
Table C-3.3.5	Incidence rate of serious adverse events by organ system, AT population, Diagnosis confirmed by surgery
Table C-3.3.6	Incidence rate of serious adverse events by organ system, AT population, Diagnosis based on clinical symptoms
Table C-3.3.7	Incidence rate of serious adverse events by organ system, AT population, Germany
Table C-3.3.8	Incidence rate of serious adverse events by organ system, AT population, Poland
Table C-3.3.9	Incidence rate of serious adverse events by organ system, AT population, Hungary
Table C-3.3.10	Incidence rate of serious adverse events by organ system, AT population, Switzerland
Table C-3.3.11	Incidence rate of serious adverse events by organ system, AT population, Russia
Table C-3.3.12	Incidence rate of serious adverse events by organ system, AT population, Ukraine

Supporting document SOP BMT 01.09 – Doc 5002.02 – Effective date 21.03.2017

#### Section C-3.4 Incidence rate of serious adverse events by organ system for long-term use

Table C-3.4.1 Incidence rate of serious adverse events by organ system for long-term use, AT population, Complete cohort

	DNG		OAED			NAED		Ex-use	Allocation unknown	Total
		GnRH-a	Danazol	All OAED	СНС	Other progestin	All NAED			
Number of women years*	XX	xx								
Serious adverse events**	xx	xx								
IR (95% CI) Thereof***	xx.x (xx.x-x.x)	xx.x (xx.x-x.x)	xx.x (xx.x–x.x)	xx.x (xx.x–x.x)	xx.x (xx.x-x.x)	xx.x (xx.x–x.x)	xx.x (xx.x–x.x)	xx.x (xx.x–x.x)	xx.x (xx.x-x.x)	xx.x (xx.x–x.x)
Infectious diseases	XX		XX	XX	XX		XX	XX	XX	XX
Neoplasms, malignant	xx	xx	xx.x (xx.x–x.x)	xx	XX	XX	xx.x (xx.x–x.x)	xx.x (xx.x–x.x)	xx	xx
Neoplasms, benign	xx	xx	xx.x (xx.x–x.x)	xx	xx		xx	xx.x (xx.x–x.x)	xx.x (xx.x–x.x)	xx
Diseases of the blood	xx.x (xx.x–x.x)	,	xx.x (xx.x–x.x)	xx.x (xx.x–x.x) xx	xx.x (xx.x–x.x)	xx.x (xx.x–x.x)	xx.x (xx.x–x.x)	xx.x (xx.x–x.x) xx	xx.x (xx.x–x.x) xx	xx.x (xx.x–x.x)
and blood-forming organs Endocrine diseases	xx.x (xx.x–x.x)		xx.x (xx.x–x.x)	xx.x (xx.x-x.x)	xx.x (xx.x–x.x)					
	xx.x (xx.x-x.x)	xx.x (xx.x–x.x)	xx.x (xx.x-x.x)	xx.x (xx.x-x.x)	xx.x (xx.x-x.x)					
Psychiatric and neurological disorders	xx xx.x (xx.x-x.x)	xx xx.x (xx.x–x.x)	xx xx.x (xx.x–x.x)	xx xx.x (xx.x–x.x)	xx xx.x (xx.x-x.x)		xx xx.x (xx.x–x.x)	xx xx.x (xx.x–x.x)	xx xx.x (xx.x–x.x)	xx.x (xx.x–x.x)
Eye	xx xx.x (xx.x-x.x)		xx xx.x (xx.x–x.x)	xx.x (xx.x-x.x)						
Ear	xx xx.x (xx.x–x.x)	xx.x (xx.x–x.x)								
Cardiovascular system	xx	xx	xx xx.x (xx.x–x.x)	xx	xx	, ,	xx	xx xx.x (xx.x–x.x)	xx	xx
Respiratory system	xx	xx	xx (xx.x-x.x)	xx	XX	xx	xx xx.x (xx.x-x.x)	xx xx.x (xx.x–x.x)	xx	xx

Supporting document SOP BMT 01.09 - Doc 5002.02 - Effective date 21.03.2017

Digestive system	xx			
	xx.x (xx.x-x.x)			
Skin	XX			
	xx.x (xx.x-x.x)			
Musculoskeletal system	xx			
and connective tissue	xx.x (xx.x-x.x)			
Genitourinary system	xx			
	xx.x (xx.x-x.x)			
Pregnancy, delivery and	xx			
Puerperium	xx.x (xx.x-x.x)			
Injury, poisoning,	xx			
accidents etc.	xx.x (xx.x-x.x)	xx.x (xx.x-x.x)	xx.x (xx.x–x.x)	xx.x (xx.x-x.x)

Note: \* Only women with 15 months or more of continuous EMT intake were considered. Incidence rates are calculated based on an observation time of 15 months or more

Note: \*\* Incidence rate is shown per 104 women years.

SAEs, which occurred within 3 months after stop of EMT, were attributed to the last EMT used by the women. Therefore, pregnancy-related SAEs in XXX cohorts does not necessarily reflect unwanted pregnancies during

Note: \*\*\* Women may appear in more than one category. ICD10 Codes Version 2009.

Table C-3.4.2	Incidence rate of serious adverse events by organ system for long-term use, AT population, Starter
Table C-3.4.3	Incidence rate of serious adverse events by organ system for long-term use, AT population, Switcher
Table C-3.4.4	Incidence rate of serious adverse events by organ system for long-term use, AT population, Restarter
Table C-3.4.5	Incidence rate of serious adverse events by organ system for long-term use, AT population, Diagnosis confirmed by surgery
Table C-3.4.6	Incidence rate of serious adverse events by organ system for long-term use, AT population, Diagnosis based on clinical symptoms
Table C-3.4.7	Incidence rate of serious adverse events by organ system for long-term use, AT population, Germany
Table C-3.4.8	Incidence rate of serious adverse events by organ system for long-term use, AT population, Poland
Table C-3.4.9	Incidence rate of serious adverse events by organ system for long-term use, AT population, Hungary

- Table C-3.4.10 Incidence rate of serious adverse events by organ system for long-term use, AT population, Switzerland
- Table C-3.4.11 Incidence rate of serious adverse events by organ system for long-term use, AT population, Russia
- Table C-3.4.12 Incidence rate of serious adverse events by organ system for long-term use, AT population, Ukraine

Supporting document SOP BMT 01.09 – Doc 5002.02 – Effective date 21.03.2017

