#### 1.1 Rationale and background

Dienogest (DNG) is a 19-nortestosterone derivative progestogen that is highly selective for progesterone receptors [1]. As a progestin in DNG/EE, DNG is known for having strong endometrial effects that improve dysmenorrhea and decrease the duration of menstrual bleeding [2]. In addition, progestogens may also modulate pain associated with endometriosis by dampening neuronal activity [3]. It is not known what influence DNG will have on bleeding disturbances associated with endometriosis over a longer time frame or the potential influence of DNG on mood disturbance and depression in endometriosis patients.

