#### Risk of long-term use

- 1. Selected baseline characteristics in long-term user
- 2. Anemia (primary outcome) in long-term user
- 3. Depression (primary outcome) in long-term user
- 4. SAEs in long-term user

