#### 6.1 Data coding

Disease diagnoses are coded using the  $ICD10^{12}$  (International Classification of Diseases). Additional codes are used for the coding of events that are of specific interest.

Concomitant medication is coded using WHO ATC-Codes. Surgical procedures are coded using the modified operation and procedure coding list (OPS) provided by DIMDI (German Institute for Medical Documentation and Information). All other relevant information will be coded by a ZEG specific, highly standardized coding system (ZEG Coding Dictionary). All outcomes of interest are additionally described in a case narrative, the "case summary".

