#### Serious adverse events

Incidence rate of SAEs by organ system (complete cohort and long-term user)

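### The long-term SAE table (C-3.4.1) pools psychiatric with neurological events that the all-user table (C-3.3.1) reports separately, so serious psychiatric events outside confirmed depression have no rate of their own in long-term users

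*SAP*

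**What the plan says.** SAP section 8 (Structure of the Analysis Tables, Section C-3) plans one kind of SAE table for two groups: "Incidence rate of SAEs by organ system (complete cohort and long-term user". The two shells do not have the same rows.

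- **Table C-3.3.1, all users.** Mental disorders have their own row, whose label is split over two lines and ends in "behavioral disorders". The next row is "Disease of the nervous system".
- **Table C-3.4.1, long-term users.** A single row covers both: "Psychiatric and neurological disorders".

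Both tables carry the same footnote: "Women may appear in more than one category. ICD10 Codes Version 2009". SAP 6.1 (Data coding) confirms ICD-10 as the source of the diagnoses. SAP 5.4.4 (Risk of long-term use) names "SAEs in long-term user" as a secondary outcome, listed separately from anemia and depression in the same women. SAP 6.2.2 defines a long-term user by at least 15 months of continuous treatment.

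**The concern.** The effect on mood is one of the reasons for the study. SAP 1.1 names as unknown "the potential influence of DNG on mood disturbance and depression in endometriosis patients", and long-term safety is a named objective. In such a study one would expect the SAE table for long-term users to show psychiatric events at least as clearly as the table for everyone. It shows them less clearly.

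Two things are at stake. An excess of psychiatric SAEs in one long-term cohort would be averaged with neurological SAEs, for which no effect is expected, and so pulled towards no difference. A reader who wants to know whether the psychiatric SAE rate in long-term users differs from that in all users would also find different rows in the two tables.

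**Working it through.** **Step 1. Is the mismatch real?** The pooled label in C-3.4.1 is legible and reads as a chosen row name, so it is not damage from text extraction. Eye and ear have separate rows in both tables, so the pooling concerns only the psychiatric and nervous-system categories. Both tables cite the same ICD-10 version and the same counting rule, and neither gives a reason for the difference.

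**Step 2. What does the pooled row hide that is not shown elsewhere?**

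- Confirmed depression in long-term users has its own tables, C-2.6.1 to C-2.6.12. They correspond to the all-user tables C-1.2.2 to C-1.2.13.
- That definition is narrow. Under SAP 5.4.3, apart from suicide or attempted suicide, a case needs a diagnosis by a physician specialized in psychiatry. Bipolar and schizoaffective disorders are excluded. Protocol Appendix 1 classes a diagnosis by a physician without psychiatric training as not confirmed.
- A psychiatric event outside the definition is still an SAE if it leads to inpatient admission (SAP 5.4.5).
- For all users, such events appear in the mental-disorders row of C-3.3.1. The self-reported depression table (C-4.3.1 in the list of tables, C-3.10.1 in the shells) also breaks down unconfirmed reports, with rows for cases treated by a general practitioner and for other psychiatric disorders, including anxiety and bipolar disorder.
- The self-reported table is stratified by user type, diagnosis classification and country. It has no long-term version.

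For long-term users, the pooled row of C-3.4.1 is therefore the only organ-system row in which these events appear, and nothing in that table separates them.

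**Step 3. How much could pooling dilute a signal?** The shells hold only placeholders, and the documents give no split between psychiatric and neurological SAEs. The following is an illustration on assumed values.

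- Let the reference rate of psychiatric SAEs be 1 unit and that of neurological SAEs be k units.
- Suppose the exposed cohort has twice the psychiatric rate and the same neurological rate.
- Pooled rate ratio = (2 + k) / (1 + k).

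| k (neurological : psychiatric) | Calculation | Pooled ratio |
|---|---|---|
| 0.25 | 2.25 / 1.25 | 1.80 |
| 0.5 | 2.5 / 1.5 | 1.67 |
| 1 | 3 / 2 | 1.50 |
| 3 | 5 / 4 | 1.25 |

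For any k above zero the pooled ratio lies between 1 and the true psychiatric ratio of 2. The direction is certain under these assumptions. The size depends on k, which is unknown.

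**Step 4. Can the two tables still be compared?** Only approximately. The two C-3.3.1 rows can be added to approximate the pooled row. If the rows count women, the sum is an upper bound and the larger row a lower bound for the number with either kind of event, because a woman may appear in both. This works in one direction only: C-3.4.1 gives no means of recovering a psychiatric rate for long-term users.

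**The case against.** The strongest reply is that the study's psychiatric question is depression, and depression is handled properly. A reader might infer from the pooled row that serious psychiatric harm under long-term DNG is lost altogether. The documents do not support that. New or worsening depression in long-term users is a separate secondary outcome with its own tables. Its definition includes suicide and attempted suicide. The all-user depression shell (C-1.2.1) has rows for psychiatrist treatment, hospital admission, suicide attempt and suicide, although no shell is printed for C-2.6. Table B-8.10.1 also follows the mood score to 84 months in women who stayed on their baseline treatment. This part of the reply stands. What remains is the group of serious psychiatric events that are not confirmed depression.

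A reader might also infer that the two SAE tables cannot be compared at all. That goes too far, because the two all-user rows can be added. Comparisons between cohorts within C-3.4.1 do not depend on C-3.3.1. The SAE tables are descriptive, and SAP Section D confines inferential comparisons to the primary outcomes. C-3.4.1 also uses a different time base (observation of 15 months or more), so matching rows would not make the two tables a formal contrast.

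Nor does anything rest on the lack of a malformations row in the long-term table, since malformations of the newborn have their own table, C-3.6.1.

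Finally, the plan assumes a 20% prevalence of depression in this population, so psychiatric events may outnumber neurological ones. That is a fair reason to include k below 1, where dilution is milder, and the table above does so.

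None of this explains why the long-term shell has the coarser row.

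**Conclusion.** The point holds as a minor inconsistency with a real but limited consequence. In long-term users, serious psychiatric events outside confirmed depression have no separable rate, although long-term SAEs are a named secondary outcome and the same events have their own row for all users. The row can be compared with C-3.3.1 only approximately.

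On the assumption that psychiatric SAEs double and neurological SAEs do not change, the pooled ratio falls from 2 to between 1.80 (k = 0.25) and 1.25 (k = 3). Both the doubling and the range of k are assumptions, and the documents supply neither. No primary hypothesis, sample size or test is affected, and confirmed depression under long-term use remains reported.

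**What to change.** In SAP mock Tables C-3.4.1 to C-3.4.12, replace the pooled row with the two rows used in C-3.3.1, one for mental and behavioral disorders and one for diseases of the nervous system. It would also help to state that the C-2.6 tables use the C-1.2.1 shell, so that its severity rows are shown for long-term users.

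This is an edit to table shells only. The diagnoses are already coded in ICD-10, so no new data, coding or analysis decision is needed. The change is best made before the tables are produced, because splitting the row after results are known could look data-driven.
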